# 1. BACKGROUND AND DESIGN

The trial hypothesis under investigation is that treatment with aspirin is safe and improves important surrogate clinical outcomes in adult patients with ARDS.

The objective of the trial is

1. To conduct a prospective randomised, double-blind, allocation concealed, placebo-controlled phase 2 trial of aspirin as a treatment for ARDS.
2. To study the biological effects of aspirin on pulmonary and systemic
  - a. inflammatory responses,
  - b. epithelial and endothelial function and injury and
  - c. lipid inflammatory mediators

Subjects will be randomised to receive aspirin 75mg capsule or a placebo capsule enterally for up to 14 days. Subjects will be randomised in a 1:1 ratio using blocks of variable size. The first dose of the study drug will ideally be administered within 4 hours of randomisation and subsequent doses will be as close to 10 am as possible starting on the following calendar day.

Patients will be eligible to participate in the study if they fulfil the following criteria:

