**Table.1. Data Completion Schedule**

CRF	Day									
	0	1	2-3	4	5-6	7	8-13	14	15- 42	90
Eligibility assessment	X									
Informed consent	X									
Randomisation	X									
Baseline data	X									
Daily data		X	X	X	X	X	X	X		
Study drug administration		X	X	X	X	X	X	X		
Adverse events		X	X	X	X	X	X	X	X	
BAL sampling	X			X						
Blood sampling	X			X		X		X		
Urine sampling	X			X		X		X		
Clinical Outcome									X	X

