## 6. ANALYSIS PRINCIPLES

Primary outcome measure is the OI at day 7. Unadjusted (primary analysis) and adjusted analysis will be carried out to test whether there is a statistically significant difference between the aspirin & placebo groups. Secondary analysis will be carried out, if the day 7 OI values are missing, using last value carry forward method.

Secondary outcome measures are OI, CRs, PF ratio, and SOFA score at day 4, 7, 14 and safety. Unadjusted and adjusted analysis will be carried out on OI, CRs, PF ratio, SOFA score, to test whether there is a statistically significant difference between the groups.

Unadjusted analysis will be carried out using Independent sample t-test. Adjusted analysis will be carried out using ANCOVA or [mixed modelling technique](#), based the number of data points available at each time point. Estimates & 95% confidence interval will be reported.

The number of AE, ARs, SAE, SARs, SUSARs and number (%) of patient experiencing the events will be reported. Fisher's exact test and proportion test will be used to check whether incidences of adverse events differ between the groups. Relative risk and 95% CI will be reported.

Exploratory analysis on mediators will be carried out using student t-tests or non-parametric alternative and Fishers Exact Test, presented by day where applicable. The estimates & 95% CIs will be reported. Statistical diagnostic methods will be used to check for violations of the assumptions, and transformations will be performed if required. For binary outcome measures, risk ratios and associated 95% CI will be calculated. Survival analysis technique will be used for time-to-event data. Median survival time & 95% CI will be estimated using Kaplan-Meier estimation method and the Kaplan-Meier plots will be presented. In all time-to-event analyses, patients that did not experience the event in question (e.g. death) were censored on the date last seen or 90 days. The equality of survivorship function of aspirin & placebo group will be tested

for significance using a log-rank  $\chi^2$  test. Hazard ratios (HRs) & 95% CIs will be reported if the proportionality assumption holds.

Correlations between changes in the biological markers measured and physiological and clinical outcomes will be assessed by appropriate graphical and statistical methods including Pearson's (or Spearman's) correlation coefficient.

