Lowest eGFR mL/min									
	Aspirin	n	xx.x ± x.x	n	xx.x ± x.x	n	xx.x ± x.x	n	xx.x ± x.x
	Placebo	n	xx.x ± x.x	n	xx.x ± x.x	n	xx.x ± x.x	n	xx.x ± x.x
	p-value #			0.xxx		0.xxx		0.xxx	

# p values for ANCOVA or mixed model

**Table A 2.. Adverse events/reactions (AE/AR), serious adverse events/reactions (SAE/SAR) & suspected unexpected serious adverse reactions**

		Number of Events			Number of Patients				
		Total	Aspirin	Placebo	Total N=<n>	Aspirin N=<n>	Placebo N=<n>	RR (95%I)	p-values
AE/AR, SAE/SAR and SUSAR	Total number of adverse events (AEs)	n	n	n	n (%)	n (%)	n (%)	x.xx (x.xx to x.xx)	x.xx
	Total number of adverse reactions (ARs)	n	n	n	n (%)	n (%)	n (%)	x.xx (x.xx to x.xx)	x.xx
	Total number of serious adverse events (SAEs)	n	n	n	n (%)	n (%)	n (%)	x.xx (x.xx to x.xx)	x.xx
	Total number of serious adverse reactions (SARs)	n	n	n	n (%)	n (%)	n (%)	x.xx (x.xx to x.xx)	x.xx
	Total number of events related to study drug and unexpected (SUSAR)	n	n	n	n (%)	n (%)	n (%)	x.xx (x.xx to x.xx)	x.xx
AEs	Blood and lymphatic system disorders	n	n	n	n (%)	n (%)	n (%)	x.xx (x.xx to x.xx)	x.xx
	Cardiac disorders	n	n	n	n (%)	n (%)	n (%)	x.xx (x.xx to x.xx)	x.xx
	Gastrointestinal disorders	n	n	n	n (%)	n (%)	n (%)	x.xx (x.xx to x.xx)	x.xx
	Hepatobiliary disorders	n	n	n	n (%)	n (%)	n (%)	x.xx (x.xx to x.xx)	x.xx
	General disorders and administration site conditions	n	n	n	n (%)	n (%)	n (%)	x.xx (x.xx to x.xx)	x.xx
	Infections and infestations	n	n	n	n (%)	n (%)	n (%)	x.xx (x.xx to x.xx)	x.xx
	Injury, poisoning and procedural complications	n	n	n	n (%)	n (%)	n (%)	x.xx (x.xx to x.xx)	x.xx
	Musculoskeletal and connective tissue disorders/Elevated Creatinine Kinase	n	n	n	n (%)	n (%)	n (%)	x.xx (x.xx to x.xx)	x.xx
	Investigations	n	n	n	n (%)	n (%)	n (%)	x.xx (x.xx to x.xx)	x.xx
	Nervous system disorders	n	n	n	n (%)	n (%)	n (%)	x.xx (x.xx to x.xx)	x.xx
	Renal and urinary disorders	n	n	n	n (%)	n (%)	n (%)	x.xx (x.xx to x.xx)	x.xx
	Respiratory, thoracic and mediastinal disorders	n	n	n	n (%)	n (%)	n (%)	x.xx (x.xx to x.xx)	x.xx
Skin and subcutaneous tissue disorders	n	n	n	n (%)	n (%)	n (%)	x.xx (x.xx to x.xx)	x.xx	
SAEs	Blood and lymphatic system disorders	n	n	n	n (%)	n (%)	n (%)	x.xx (x.xx to x.xx)	x.xx
	Cardiac disorders	n	n	n	n (%)	n (%)	n (%)	x.xx (x.xx to x.xx)	x.xx
	Gastrointestinal disorders	n	n	n	n (%)	n (%)	n (%)	x.xx (x.xx to x.xx)	x.xx
	Hepatobiliary disorders	n	n	n	n (%)	n (%)	n (%)	x.xx (x.xx to x.xx)	x.xx

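### Mediators are compared between arms only by unadjusted tests at each day, although day-0 samples are scheduled and the SAP uses ANCOVA or mixed models elsewhere; the cost is precision, not validity

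*SAP*

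**What the plan says.** The second trial objective in SAP section 1 is mechanistic: "To study the biological effects of aspirin on pulmonary and systemic" inflammatory responses, epithelial and endothelial function and injury, and lipid mediators. Section 2.3 places the corresponding analyses under an exploratory heading.

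For comparing the arms on these markers, section 6 gives one instruction: "Exploratory analysis on mediators will be carried out using student t-tests or non-parametric alternative and Fishers Exact Test, presented by day where applicable". The same paragraph promises estimates with 95% confidence intervals, diagnostic checks, and transformations if needed. It names no baseline covariate, change score, ANCOVA or mixed model for the mediators.

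Elsewhere the SAP does adjust:
- For the physiological outcomes: "Unadjusted and adjusted analysis will be carried out on OI, CRs, PF ratio, SOFA score". The method follows: "Adjusted analysis will be carried out using ANCOVA or" mixed modelling.
- For the routine laboratory values in Table A7, which include CRP and fibrinogen, the footnote reads "p values for ANCOVA or mixed model". Tables A5 and A6 carry the same footnote for oxygenation parameters and fluid balance.

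In Table 1 (section 3.3), the rows "Blood sampling" and "Urine sampling" are marked at days 0, 4, 7 and 14, and the BAL row at days 0 and 4. Section 7.2 says that randomisation is stratified by vasopressor requirement.

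**The concern.** Every sampled fluid has a scheduled pre-treatment measurement, so each mediator can in principle be adjusted for its own starting value. The plan does not use that value when it compares the arms. A routine CRP gets an ANCOVA or mixed-model p-value, while the research inflammatory markers, which serve a stated objective, get a plain two-sample test.

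The trial has at most 30 patients per arm, and probably fewer with a day-4 BAL or a day-14 blood sample. At that size, differences between patients that were already present at baseline can make up much of the spread at follow-up. Leaving them in widens the intervals on which the mechanistic conclusions will rest. Adjustment added after unblinding would be open to the charge that the results drove the choice, so the place to settle it is the SAP.

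**Working it through.** **1. The plan's own figure.** Section 5 gives a difference of 39, an SD of 51, two-sided 0.05, 80% power and 28 per arm for OI at day 7. The standardised difference is 39/51 = 0.765. The noncentral t-test with 28 per arm (54 df, noncentrality 0.765 × √(28/2) = 2.86) has 80.2% power; 27 per arm has 78.7%. With 5% drop-out, 28/0.95 = 29.5, so 30 per arm and 60 in all. The stated figures reproduce. The SAP states no power or precision for mediators.

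**2. Inputs for the mediators.** From the SAP: 1:1 allocation, two-sided 0.05, 28 evaluable per arm. Assumed, because the SAP gives no value:
- r, the correlation of a mediator's day-0 and follow-up values, from 0 to 0.7;
- 15 per arm as an example of a reduced sample set such as day-4 BAL;
- the vasopressor stratum explains nothing beyond the day-0 value, which is unfavourable to adjustment.

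**3. Formulas, with n per arm.**
- t-test: SE = SD × √(2/n), with 2n − 2 df.
- ANCOVA with two covariates: SE = SD × √(VF × 2/n), with 2n − 4 df and VF = (1 − r²) × (1 + 2/(2n − 5)).

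The second factor of VF charges for estimating two covariates. It is 1 + 2/51 = 1.039 at n = 28 and 1 + 2/25 = 1.080 at n = 15. For example, at n = 28 and r = 0.5, VF = 0.75 × 1.039 = 0.779. The ANCOVA is then worth a t-test with 28/0.779 = 36 per arm.

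**4. Results.** The t-test detects 0.76 SD (n = 28) or 1.06 SD (n = 15) with 80% power. For ANCOVA, the power shown is at that same difference.

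| r | VF, n = 28 | Detectable, SD | Power | VF, n = 15 | Detectable, SD | Power |
|---|---|---|---|---|---|---|
| 0 | 1.039 | 0.78 | 78% | 1.080 | 1.10 | 77% |
| 0.3 | 0.946 | 0.74 | 82% | 0.983 | 1.05 | 80% |
| 0.5 | 0.779 | 0.67 | 89% | 0.810 | 0.96 | 87% |
| 0.7 | 0.530 | 0.56 | 97% | 0.551 | 0.79 | 96% |

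The two methods break even at r of about 0.20 with 28 per arm and 0.28 with 15 per arm.

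**5. Missing day-0 samples.** Suppose 15 per arm have a day-4 BAL but 3 of them per arm lack the day-0 BAL (assumed). A complete-pairs ANCOVA then has 12 per arm. At r = 0.5, VF = 0.75 × (1 + 2/19) = 0.829, and the detectable difference is 1.09 SD, slightly worse than 1.06 SD for the t-test on all 15. Adjustment without a rule for missing baselines can therefore lose what it was meant to gain.

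**The case against.** The strongest reply is that this is a preference about efficiency. A two-sample test on post-baseline values is valid under randomisation, and its p-value and interval already allow for chance baseline differences. That stands. A reader might infer that baseline imbalance biases the mediator results or inflates their type I error. The documents do not support this, because in a randomised comparison imbalance adds variance and nothing more.

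It can also be said that the gain depends on an r that the SAP does not supply, and that it is small or absent when r is low and samples are few. This stands too: at 15 per arm and r = 0.3 the gain is negligible (1.05 against 1.06 SD).

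A reader might further infer that the day-0 values go unused. They do not: the SAP also says "Correlations between changes in the biological markers measured and physiological and clinical outcomes will be assessed". But that analysis relates markers to outcomes and gives no baseline-adjusted difference between the arms. Likewise, the permitted transformations and rank tests deal with the shape of the distribution, not with baseline.

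The exploratory label limits how serious the point is. It does not explain the different treatment, since the laboratory and fluid-balance variables are not named efficacy outcomes either and still receive ANCOVA or mixed models.

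**Conclusion.** The point holds as a minor one. The SAP fixes unadjusted by-day tests for the mediators, has day-0 samples scheduled for every fluid, and plans adjusted methods for comparable variables without stating why mediators differ. The consequence is a probable loss of precision for a stated objective. It does not make the tests invalid, and the primary result is not affected.

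The size cannot be fixed from the document. Over an assumed r of 0.3 to 0.7, adjustment lowers the detectable difference by 0.02 to 0.20 SD at 28 per arm (0.76 to between 0.74 and 0.56) and by 0.01 to 0.27 SD at 15 per arm (1.06 to between 1.05 and 0.79). The risk is lopsided: if baseline predicts nothing, power drops only from 80% to about 78% or 77%. It would go too far to say that precision is certainly lost or that the choice has no justification; what can be said is that none is stated.

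**What to change.** Amend the mediator sentence in SAP section 6 along these lines:
- Compare each continuous mediator at each post-baseline day by ANCOVA, adjusted for its day-0 value and the vasopressor stratum. For blood and urine, a mixed model over days 4, 7 and 14 with the same covariates is an alternative; BAL has day 4 only.
- Use the log scale where the SAP's existing diagnostics call for it, and then report a geometric mean ratio with 95% CI. Imposing logs on every marker is unnecessary.
- State how patients without a day-0 sample stay in the comparison. One option is to impute the pooled mean baseline, blind to arm, as a declared exception to the sentence in section 3.4 that rules out imputation. Another is a constrained longitudinal model.
- Keep the unadjusted t-test or rank test as a supportive check, and Fisher's exact test for binary markers.

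The cost is SAP wording and a little more programming, with no new data. The downside is the small power loss shown above if baseline correlation proves low.

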### **2.2 Secondary outcome measures**

The following secondary clinical outcomes will also be assessed:

1. OI at days 4 and 14
2. Physiological indices of ARDS, as measured by respiratory compliance (CRs) and P/F ratio on days 4, 7 and 14
3. Organ failure as measured by change in sequential organ failure assessment (SOFA) score from baseline to days 4, 7 and 14
4. Safety and tolerability as assessed by the occurrence of adverse events/reactions (AE/AR), serious adverse events/reactions (SAE/SAR) and suspected unexpected serious adverse reactions (SUSAR).

Outcomes will be measured at baseline and daily up to day 14 or until the patient is discharged from ICU or the patient dies. Although duration of ventilation, ventilation free days at day 28 and 28 and 90-day mortality as well as length of ICU stay will be recorded, these important clinical outcomes are not included as major outcome measures as the study is not adequately powered to assess these outcomes.

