## 4. DEFINITION OF TERMS

Term	Definition
Vasopressors	Vasopressors are defined as any inotropic/vasopressor agent except dopamine < 6mcg/kg/min.
SAP II	New Simplified Acute Physiology Score
Murray Lung Injury Score	Scoring system using radiology, PF ratio, PEEP and respiratory compliance to assess the extent of adult lung injury.
APACHE II score	Acute Physiology and Chronic Health Evaluation II score. A disease severity classification system.
Predicted Body Weight (Kg)	$PredictedBodyWeight = \begin{cases} 50 + 0.91 * (Height - 152.4) & \text{for Male} \\ 45.5 + 0.91 * (Height - 152.4) & \text{for Female} \end{cases}$
Oxygenation Index (cmH 2 O/kPa)	$OI = \frac{(MAP * FiO_2)}{PaO_2} * 100$
Total SOFA Score	Guideline 13: SOFA Score v1.0 Final 04/02/2016
Respiratory Compliance (ml/cmH 2 O)	$RespiratoryCompliance = \frac{TidalVolume}{[PlateauPressure - PEEP]}$
PF ratio (kPa)	$PFRatio = \frac{PaO_2}{FiO_2}$
Unassisted breathing	Unassisted breathing is defined as; extubated with supplemental oxygen, or room air, or open T-tube breathing, or tracheostomy mask breathing, or CPAP ≤ 5 cm H 2 O without pressure support for a calendar day. Patients receiving pressure support via non-invasive ventilation will be defined as

	receiving ventilatory support. The date recorded will be the first calendar day of the final period of ventilation free days
Ventilator free days (VFDs)	
The number of days alive and free from ventilation between final successful weaning and day 28 after study enrolment.
 $VFD = \begin{cases} (28 - x), & \text{if patient alive at day 28} \wedge x \leq 27 \\ 0, & \text{if patient died within 28 days} \vee x > 27 \end{cases}$ 
Where x is number of days until patient achieved unassisted breathing

Duration of ventilation (days)	
Duration of ventilation
 $= \begin{cases} \text{Date of unassisted breathing} - \text{Date of randomisation, if the patient achieved unassisted breathing} \\ \text{Date of death} - \text{Date of randomisation, if the patient died prior} \end{cases}$ 
This calculation will be censored at day 90.

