Duration of ICU stay (days)	
Duration of ICU stay
 $= \begin{cases} \text{Date of first ICU discharge} - \text{Date of randomisation, if the patient is alive at ICU discharge} \\ \text{Date of death} - \text{Date of randomisation, if the patient died prior} \end{cases}$ 
Discharge from critical care is defined as discharge to a medical ward in the hospital or another hospital, A transfer between ICUs is not considered as a discharge from critical care. This calculation will be censored at day 90.

Duration of hospital stay (days)	
Duration of hospital stay
 $= \begin{cases} \text{Date of first hospital discharge} - \text{Date of randomisation, if the patient is alive at hospital discharge} \\ \text{Date of death} - \text{Date of randomisation, if the patient died prior} \end{cases}$ 
Hospital discharge is the first date that the patient is discharged to home/community, a transfer between hospitals is not considered as a hospital discharge. This calculation will be censored at day 90.

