**Table A 6. Survival data and length of ventilation and stay data**

	Aspirin	Placebo	p value
Ventilator free days (days)	n; xx.x ± x.x	n; xx.x ± x.x	0.xxx
Duration of ventilation (days)			
All patients	n; xx.x ± x.x	n; xx.x ± x.x	0.xxx
ICU survivors	n; xx.x ± x.x	n; xx.x ± x.x	0.xxx
ICU non-survivors	n; xx.x ± x.x	n; xx.x ± x.x	0.xxx
Duration of ICU stay (days)			
All patients	n; xx.x ± x.x	n; xx.x ± x.x	0.xxx
ICU survivors	n; xx.x ± x.x	n; xx.x ± x.x	0.xxx
ICU non-survivors	n; xx.x ± x.x	n; xx.x ± x.x	0.xxx
Duration of hospital stay (days)			
All patients	n; xx.x ± x.x	n; xx.x ± x.x	0.xxx
ICU survivors	n; xx.x ± x.x	n; xx.x ± x.x	0.xxx
ICU non-survivors	n; xx.x ± x.x	n; xx.x ± x.x	0.xxx
All-cause mortality 28 days post randomisation	n (xx.x%)	n (xx.x%)	0.xxx
All-cause mortality 90 days post randomisation	n (xx.x%)	n (xx.x%)	0.xxx

Mean ± SD & n (%) presented for treatment arms

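### Ventilation, ICU and hospital durations end at death and are then compared as means with p-values, so earlier deaths can look like shorter durations; the survivor and non-survivor tests do not repair this.

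*SAP*

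**What the plan says.** Section 4 (Definition of Terms) defines duration of ventilation, ICU stay and hospital stay in the same way. For patients who reach unassisted breathing or leave alive, it is the interval from randomisation to that date. Otherwise it is date of death minus "Date of randomisation, if the patient died prior". For each of the three it adds: "This calculation will be censored at day 90".

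The survival and length-of-stay table in Appendix 1 (headed Table A 6, although the fluid balance table is also A6) gives each duration by arm as mean ± SD with a p-value, in three rows: all patients, ICU survivors, and "ICU non-survivors". The test behind the p-value is not named.

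Section 6 (Analysis Principles) gives a general rule for time-to-event data. "Median survival time & 95% CI will be estimated using Kaplan-Meier estimation method", the arms are compared "for significance using a log-rank" statistic, and "patients that did not experience the event in question (e.g. death) were censored on the date last seen or 90 days". It does not list the endpoints covered.

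Ventilator-free days (VFDs) treat death differently: section 4 scores them 0 "if patient died within 28 days". Section 2.2 says of VFDs, duration of ventilation, ICU stay and mortality that "these important clinical outcomes are not included as major outcome measures as the study is not adequately powered to assess these outcomes".

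**The concern.** Under the section 4 definitions, a patient who dies on day 3 has the same duration as one who is weaned or discharged on day 3. A mean over all patients therefore mixes a good outcome with the worst one. If one arm has more early deaths, its mean falls even though nobody recovers faster, and the p-value beside it invites the reader to take that as benefit.

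The split by ICU survival does not cure this. Survival is an outcome that aspirin may affect, so survivors in the two arms need not be comparable and the test loses the protection of randomisation. In the non-survivor row, a patient who dies before first leaving the ICU contributes the time from randomisation to death to both the ICU and the hospital duration, so a shorter value there means an earlier death.

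It is also unclear which method governs these outcomes. Censoring at day 90 is time-to-event language, but the table shell shows plain means. If the Kaplan-Meier rule in section 6 is meant to cover weaning and discharge, it makes no separate provision for death, and a death would be censored as though that patient could still be weaned or discharged later.

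**Working it through.** The SAP gives no death, weaning or discharge rate, and no figure of its own on this point to reproduce. The definitions below come from the SAP; every rate is an assumption.

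**1. Death as the end of the duration.** Assume a constant liberation hazard a = 0.07/day in both arms and a share m dying before liberation. The death hazard is d = a·m/(1 − m), and the mean duration is 1/(a + d) = (1 − m)/a.
- m = 25%: 0.75/0.07 = 10.7 days
- m = 40%: 0.60/0.07 = 8.6 days

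The more lethal arm looks 2.1 days better at an identical liberation hazard. The ratio 0.60/0.75 = 0.80 does not depend on a: the means are 15.0 v 12.0 days at a = 0.05, and 7.5 v 6.0 at a = 0.10. The day-90 limit is immaterial at a = 0.07 (for m = 25%, 1 − e^(−90 × 0.0933) = 0.9998).

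**2. A second set of assumptions, with the day-90 limit built in.** Take a = 0.05/day. Mean = (1 − e^(−90(a+d)))/(a+d). Cumulative incidence of discharge alive (or weaning) by day 28 = a/(a+d) × (1 − e^(−28(a+d))). One minus Kaplan-Meier with deaths censored = 1 − e^(−28a).

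| d per day | Dead by day 90 | Mean duration | True incidence, day 28 | 1 − KM, day 28 |
|---|---|---|---|---|
| 0.01 | 16.6% | 16.6 days | 67.8% | 75.3% |
| 0.03 | 37.5% | 12.5 days | 55.8% | 75.3% |

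The second row has a mean 4.1 days shorter, while 12.0 percentage points fewer patients leave alive by day 28.

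**3. Deaths censored, if section 6 applies.** With a = 0.07 and m = 30%, d = 0.07 × 0.30/0.70 = 0.03.
- True incidence at day 28: 0.7 × (1 − e^(−2.8)) = 65.7%
- 1 − KM at day 28: 1 − e^(−1.96) = 85.9%
- Median by KM: ln 2/0.07 = 9.9 days
- Day on which half are truly liberated: solve 0.7 × (1 − e^(−0.1t)) = 0.5, giving t = 12.5

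**4. Does censoring favour the deadlier arm?** Not under independent hazards. In the table above 1 − KM is 75.3% in both rows; it is too high by 7.5 and 19.5 points, which hides the harm but does not reverse it. Reversal needs deaths concentrated in slow recoverers. Example with 30 per arm: arm A has 15 discharged on day 10 and 15 on day 30. Arm B is the same, except that 10 of the slow patients die on day 7. In B, 20 remain at risk on day 10, so KM gives 15/20 = 75% discharged against 50% in A, although 15 of 30 have left in each arm.

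**5. What VFDs would show in step 1.** Assuming no deaths between liberation and day 28, mean VFD = a × [28/(a+d) − (1 − e^(−28(a+d)))/(a+d)²].
- m = 25%: 0.07 × (300 − 106.4) = 13.6 days
- m = 40%: 0.07 × (240 − 70.7) = 11.9 days

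VFDs move in the direction of harm.

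**The case against.** Several points on the other side stand.

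- **Scope of section 6.** Its only example of an event is death, for which the censoring rule is correct. It names no weaning or discharge endpoint, and the only output shown for the durations is mean ± SD. A reader might infer that the SAP prescribes two contradictory rules, or that it plans to censor deaths in a weaning analysis. The text supports neither: the two treatments of death are alternatives, and the SAP leaves open whether the second applies here at all.
- **Direction of the Kaplan-Meier error.** A reader might take 86% against 66% as proof that the deadlier arm would look better. It is not. It shows overstatement within an arm; step 4 shows that reversal needs a further assumption about who dies.
- **Safeguards already present.** VFDs penalise death, and 28- and 90-day mortality appear in the same table. A careful reader would see excess deaths beside a shorter duration.
- **Importance.** Section 2.2 sets most of these outcomes apart as underpowered. In step 1, with exponential SDs and 30 per arm, the standard error is √((10.7² + 8.6²)/30) = 2.5 days. Power to detect the spurious 2.1-day difference is then about Φ(2.14/2.51 − 1.96) = 14%, so a falsely significant result is unlikely.
- **A literal duration has a use.** Days ventilated or in ICU until death describe resource use, and the tables are labelled example drafts.

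These points limit the severity. They do not justify a between-arm p-value on a mean that improves with earlier death, or tests within groups defined by survival. The draft shell is also the only place where the SAP shows how the durations are to be compared.

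**Conclusion.** The point holds for the durations as defined and tabulated: death shortens them, and the comparison of means can favour the arm with more deaths. The illustrative size is 2.1 days (10.7 v 8.6) for 25% against 40% deaths at a liberation hazard of 0.07/day. It is a 20% reduction at any constant liberation hazard that is equal in both arms, apart from a negligible effect of the day-90 limit. The p-values within ICU survivors and non-survivors are not randomised comparisons, whatever the rates.

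The Kaplan-Meier part is conditional. The SAP does not say whether section 6 governs weaning and discharge. If it does, the proportion liberated would be overstated (86% v 66% at day 28 with 30% dying first). All these rates are assumed.

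This is a modest but worthwhile correction. It does not touch the primary outcome, OI at day 7, and nothing here suggests that the trial's main conclusion would change.

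**What to change.** 1. In section 6, state which endpoints the Kaplan-Meier and log-rank methods cover, and restrict them to mortality.
2. For time to unassisted breathing, ICU discharge and hospital discharge, treat death as a competing event up to day 90. Report cumulative incidence by arm, with cause-specific hazard ratios, subdistribution hazard ratios, or both. Either choice is defensible if named in advance.
3. In the survival and length-of-stay table, take the between-arm inference from the cumulative incidence analysis. Keep durations in ICU survivors and non-survivors as description only, without p-values. Any all-patient duration that is kept should be labelled as resource use that includes time to death.

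The cost is a few sentences in the SAP, a revised table shell and a little more analysis in standard software. The dates needed are already required by the section 4 definitions, so no new data are involved. With 60 patients the hazard ratios will be imprecise and should be presented as such.

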## **2.3 Exploratory analyses**

In order to determine the potential mechanism of action of aspirin, the study will investigate the biological effect of aspirin on pulmonary and systemic:

1. Inflammatory responses
2. Indices of epithelial and endothelial function and injury
3. Lipid inflammatory mediators

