## 5. SAMPLE SIZE CALCULATIONS

The primary outcome measure is the difference in OI at day 7, between aspirin and placebo treated groups. Based on our data from a recently completed clinical trial in ARDS, the mean (standard deviation; SD) OI at day 7 in patients with ARDS is 62 (51) cmH2O/kPa. A sample size of 56 subjects (28 in each group) will have 80% power at a two-tailed significance level of 0.05 to detect a clinically significant difference of 39 cmH2O/kPa in OI between groups. In a previous phase 2 study of similar size, we have found that an intervention can demonstrate a change in OI of a similar magnitude confirming a treatment effect of this size can be achieved.

Although we anticipate few withdrawals or loss to follow-up we have allowed for this in the sample size calculation. In our previous single centre study of simvastatin in ARDS there were no withdrawals. In a multi-centre UK study of pulmonary artery catheters in ICU patients

(PAC-Man), no patients were lost to follow up, and only 3% withdrew consent after recovering competency. This is in keeping with our local data. Therefore, a drop-out rate of 5% has been estimated and the study will require a total of 60 patients (30 in each group). All calculations assume 80% power at a two-tailed significance level of 0.05.

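### The exploratory marker–outcome correlation leaves arm, baseline marker and time order unfixed, and used as named it can mislead at this sample size

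*SAP*

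**What the plan says.** SAP section 2.3 sets out marker work "In order to determine the potential mechanism of action of aspirin", covering inflammatory responses, epithelial and endothelial indices, and lipid mediators. Section 6 then gives two separate analyses.

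- **Between arms:** "Exploratory analysis on mediators will be carried out using student t-tests or non-parametric alternative and Fishers Exact Test, presented by day where applicable".
- **Marker against outcome:** "Correlations between changes in the biological markers measured and physiological and clinical outcomes will be assessed by appropriate graphical and statistical methods", which the sentence completes with "including Pearson's (or Spearman's) correlation coefficient".

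The second sentence does not mention treatment arm, baseline marker, baseline OI, or which marker interval is set against which outcome day. Nothing else in the SAP supplies these. Table A4 has terms for group, day and their interaction, but its title limits it to clinical outcomes, haemodynamic and oxygenation parameters, and laboratory variables. No draft table covers the marker–outcome link.

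Table 1 in section 3.3 schedules BAL on days 0 and 4, and "Blood sampling" and urine on days 0, 4, 7 and 14. On outcome days, section 6 states: "Secondary outcome measures are OI, CRs, PF ratio, and SOFA score at day 4, 7, 14 and safety".

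**The concern.** Three features of the marker–outcome sentence are open, and each affects what a correlation would mean.

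1. **Change scores.** The change in a marker is negatively tied to its baseline value. If the baseline marker itself predicts OI, the correlation of change with OI carries that relation with the opposite sign. It can produce a correlation where change has no link to OI, or cancel a real one.
2. **Arms pooled.** If aspirin moves a marker and OI by separate routes, pooling the arms produces a correlation with no patient-level link between the two.
3. **Timing.** Marker and outcome days overlap, and no rule says that the marker must come first.

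At stake is the reading of the only planned analysis that connects markers to outcome. Leaving these choices open across many markers and several days also leaves room to settle them after the data are seen.

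**Working it through.** **The plan's own figure.** Section 5 gives a day-7 OI SD of 51 and a difference of 39, and says "A sample size of 56 subjects (28 in each group) will have 80% power at a two-tailed significance level of 0.05". The standardised effect is 39/51 = 0.765. The normal approximation gives 2 × (1.96 + 0.84)² / 0.765² ≈ 26.8, so 27 per arm. At 28 per arm, power is 81.6% (normal) or 80.2% (noncentral t). For drop-out, 56/0.95 = 58.9, so 59, against 60 stated with equal arms. The sample size is reproduced, and N = 56 is used below.

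**Threshold.** With 54 degrees of freedom, t = 2.005, so a two-sided 5% test needs |r| ≥ 2.005/√(54 + 2.005²) = 0.263.

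**Set-up.** All marker inputs are assumptions. Marker and OI have unit variance within arm. ρ is the correlation of baseline with day-4 marker, r0 that of baseline marker with day-7 OI, and b the slope of OI on the day-4 marker given baseline. Each setting was simulated 4,000 times with 28 per arm. The Pearson correlation of marker change (day 4 minus day 0) with day-7 OI was compared with a regression of day-7 OI on day-4 marker, baseline marker and arm. In general

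corr(change, OI) = [b(1 − ρ²) − r0(1 − ρ)] / √(2 − 2ρ).

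**(a) Regression to the mean, no link (b = 0, no arm effects).** The formula reduces to −r0 × √((1 − ρ)/2). For ρ = 0.5 and r0 = 0.5 this is −0.5 × √0.25 = −0.25.

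| ρ | r0 | mean r | significant, correlation | significant, adjusted |
|---|---|---|---|---|
| 0.3 | 0.3 | −0.17 | 24.9% | 5.0% |
| 0.3 | 0.5 | −0.29 | 59.6% | 4.9% |
| 0.5 | 0.3 | −0.15 | 20.2% | 5.2% |
| 0.5 | 0.5 | −0.25 | 46.6% | 4.6% |
| 0.7 | 0.3 | −0.12 | 13.9% | 4.4% |
| 0.7 | 0.5 | −0.19 | 30.6% | 5.1% |

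With r0 positive the spurious correlation is negative: larger falls in the marker go with worse OI.

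**(b) Separate arm effects, no link (b = 0, r0 = 0, ρ = 0.5).** Aspirin shifts OI by the planned 0.765 SD and the marker by d. At ρ = 0.5 the change has unit variance within arm, so pooled r = 0.25 × 0.765 × d / √[(1 + 0.25 × 0.765²)(1 + 0.25 × d²)]. For d = 1 this is 0.191/√(1.146 × 1.25) = 0.16.

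| d | mean r | significant, correlation | significant, adjusted |
|---|---|---|---|
| 0.5 | 0.09 | 10.2% | 5.1% |
| 0.765 | 0.13 | 15.0% | 4.8% |
| 1.0 | 0.16 | 22.5% | 5.4% |

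**(c) A true link masked (ρ = 0.5, no arm effects).** The formula becomes 0.75b − 0.5r0. For b = 0.3 this is 0.225, 0.075 and −0.025 at r0 = 0, 0.3 and 0.5.

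| b | r0 | mean r | power, correlation | power, adjusted |
|---|---|---|---|---|
| 0.3 | 0 | 0.22 | 40.2% | 49.5% |
| 0.3 | 0.3 | 0.07 | 7.6% | 51.8% |
| 0.3 | 0.5 | −0.02 | 5.4% | 61.0% |
| 0.5 | 0 | 0.37 | 82.6% | 91.1% |
| 0.5 | 0.3 | 0.22 | 38.3% | 93.9% |
| 0.5 | 0.5 | 0.12 | 14.7% | 97.2% |

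**The case against.** - **The wording is open.** The coefficients are examples within a list of appropriate methods. A reader might infer that the SAP commits to a plain pooled correlation, but the text does not go that far: adjusted or within-arm analyses are left unspecified, not excluded. This stands, and it limits the point to what the SAP fails to fix and to what happens if the named coefficients are used alone.
- **Mechanism does not rest on this sentence.** A reader might infer that section 2.3 depends on the correlation. Section 2.3 asks for the biological effect of aspirin, and the randomised between-arm comparison in section 6 mainly answers that. It has none of these faults. This stands.
- **Reverse order is not planned.** A reader might suppose that marker change to day 14 will be set against day-7 OI. The SAP names no such pairing, and the shared days 4, 7 and 14 make same-day pairing at least as natural. What stands is only that the pairing is not fixed.
- **The sizes depend on assumed inputs.** Bias (a) needs a baseline marker related to OI; at r0 = 0 it vanishes. If baseline and day-4 marker both correlate 0.4 with OI, the change correlates exactly zero, but that follows from choosing them equal. With 0.5 for day 4, 0.3 for baseline and ρ = 0.5, it is (0.5 − 0.3)/√(2 − 1) = 0.20. Hence ranges are given, not one value.
- **The arm effect is modest.** Even with the full planned OI effect and a 1 SD marker shift, pooled r is 0.16, below the threshold of 0.263. That is correct; the harm is a raised error rate.
- **Adjustment does not prove mediation.** Marker and outcome can share causes after randomisation. This stands and is carried into the fix.

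**Conclusion.** The point holds as a gap in an exploratory analysis. The SAP names only unadjusted coefficients on marker change and does not fix arm, baseline marker or time order. Used that way with arms pooled, at N = 56 and with no true link, false positives are about 14–60% for r0 of 0.3–0.5 and ρ of 0.3–0.7. They are 10–23% for separate arm effects of 0.765 SD on OI and 0.5–1.0 SD on the marker. Power for a true 0.3 SD slope falls from 40% to 5–8% once r0 is 0.3–0.5. With baseline marker and arm in the model, false positives were 4.4–5.4% in every null setting of (a) and (b), and power for that slope was 50–61%.

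These figures assume 56 patients with complete data, normally distributed values and marker correlations that the SAP does not give. The model checked did not include baseline OI. The primary analysis, the sample size and the randomised marker comparisons are untouched, so this is a minor, worthwhile improvement.

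**What to change.** In SAP section 6, replace the marker–outcome sentence with text that:

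- makes the main analysis a regression, or partial Spearman correlation, of day-7 OI on the day-4 marker, adjusted for baseline marker and treatment arm, and for baseline OI if numbers allow, in patients sampled on day 4;
- shows the estimate within each arm as well;
- for any other pairing, uses a marker measured before the outcome, with the same adjustment;
- reports the result as association, not as proof that aspirin acts through the marker.

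Day 4 suits this purpose because it is the only day after baseline when Table 1 schedules BAL, blood and urine together, and it precedes the primary outcome.

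The cost is a change of SAP wording and a little more analysis, with no new samples. The downside is two or three adjustment terms beside the marker at perhaps 50 patients (an assumed number), so estimates will be imprecise and a null result will still not exclude a modest link.
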